11. RECORDING ADVERSE REACTIONS

During the entire follow-up period, the physician should report any suspicion of a serious adverse reaction observed in the patient under treatment by completing a Serious Adverse Reaction Report form, forwarding it to the coordinating center (Annex 5).

PRONOCOST study. Cost-effectiveness pharmacoeconomic study of a standardized multidisciplinary weight loss method (PronoKal® Method) to improve health condition of obese patients with associated comorbidities.

SERIOUS ADVERSE REACTION: refers to any adverse reaction that can be classified in one or more of the following categories:

- Fatal
- Life-threatening
- Causes persistent or significant disability
- Causes hospitalization or prolongs hospital stay

Congenital anomalies/birth defects and serious adverse clinical consequences associated with use under conditions other than those set out in the Summary of Product Characteristics (SmPC), overdose or abuse are also included.

Medical judgment should be implemented when deciding whether an event or reaction is serious in other situations. Major adverse reactions or events that do not pose an immediate danger to life or cause death or hospitalization but which may endanger the patient should be considered serious.

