7.2. Follow-up period

The expected follow-up period for each patient will be 2 years from the time of inclusion, recording data during the weight loss and maintenance periods. The registry of patient data for this study will be made by the doctor and the dietitians/nutritionists who will regularly see the patient in the face-to-face visits at the Pronokal centre. For this, a specific form will be designed in which information about the variables to be studied will be collected.

Before starting treatment with the standardized multidisciplinary method and its inclusion in the study, the physician will have performed a first patient pre-inclusion visit (day -15) to request complementary tests (laboratory and ECG) and rule out the existence of contraindications to the ketogenic diet part of the weight loss program.

The study will begin with the baseline visit (day 0) in which the inclusion and exclusion criteria will be confirmed, the signing of informed consent will be obtained and the multidisciplinary treatment will be prescribed, followed by 6 control visits: 2 visits during the ketogenic stage (1-month after the start and at the end of ketosis), 2 visits during the physiological adaptation phase (at 4 or 5 months and at the end of stage 2) and 2 follow-up visits during the maintenance up to the 2-year completion. Regardless of the visits established in this protocol, the doctor will make as many visits as he/she deems necessary for good patient control.

On the other hand, dietitians/nutritionists, according to the methodology of the program, will carry out a face-to-face follow-up of the patient, which will be fortnightly during the ketogenic diet, monthly during the physiological adaptation of stage 2 and quarterly or semi-annual during the maintenance stage.

In the **pre-inclusion visit (day -15)**, the physician will perform a first clinical assessment of the patient. He/she will record the sociodemographic data, history of diabetes, comorbidities, pharmacological treatments. He/she will request complete laboratory tests and will perform an electrocardiogram to rule out contraindications and verify the inclusion/exclusion criteria. The said laboratory tests will include:

- Complete blood count and leukocyte formula
- Hydrocarbon metabolism: fasting glycemia, HbA1c, insulinemia
- Lipid profile: total cholesterol, LDL-C, HDL-C, triglycerides
- Transaminases: GOT, GPT, gammaGT

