- Renal profile: creatinine, glomerular filtration, creatinine clearance, microalbuminuria
- Nitrogen balance: urea, uric acid
- Thyroid profile: TSH, T3, T4
- Ionogram: Na, K, Cl, Ca, Mg

In the **initial visit (day 0)**: In this visit, a physical examination will be performed and data related to weight (weight, BMI, waist circumference), as well as data on comorbidities associated with obesity (type of pathology, pharmacological treatment, complications in the last year) will be recorded. After checking the inclusion/exclusion criteria, the patient information sheet will be given and the informed consent will be obtained. During this visit, the patient's quality of life will be assessed (with the SF-12 quality of life questionnaire) and treatment will be prescribed according to the method (PronoKal® Method), which will begin with phase 1 of the active stage.

PRONOCOST study. Cost-effectiveness pharmacoeconomic study of a standardized multidisciplinary weight loss method (PronoKal® Method) to improve health condition of obese patients with associated comorbidities.

In the **follow-up visits - Recorded by the doctor**. In the regular check-ups throughout the course of treatment, the physician will record: any discomfort or side effect related to weight loss treatment and whether there has been any change in the comorbidities associated with obesity (laboratory results, medication, complications, etc.). At the end of each stage the doctor will assess the patient's quality of life through a questionnaire.

In the **follow-up visits - Recorded by dietitians/nutritionists**. During the interviews that the dietitians/nutritionists will have with the patients, and parallel to the doctor's records, the following details will be recorded:

- Clinical data: anthropometric data and blood pressure
- Medication changes
- Onset of complications (e.g., hypertensive crisis, ...)
- Hospital admissions
- Work absenteeism: number of days and cause....

In case of early withdrawal from the study, the doctor will write the dropout date and the reason, in study completion form.

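### Dietitians record admissions and complications but have no side-effect item, and no hand-over to the physician who reports serious reactions is stated; the gap matters mainly in maintenance

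*Combined protocol and SAP*

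**What the plan says.** Section 7.2 gives separate follow-up lists for the two groups of staff. At check-ups, "the physician will record: any discomfort or side effect related to weight loss treatment", together with changes in comorbidities, which include laboratory results, medication and complications. For dietitians/nutritionists, "parallel to the doctor's records, the following details will be recorded": anthropometry and blood pressure, medication changes, complications, hospital admissions and work absenteeism. Side effects are not on the dietitian list.

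Section 11 covers the whole follow-up period and names one reporter: "the physician should report any suspicion of a serious adverse reaction observed in the patient under treatment". The physician completes the report form (Annex 5) and forwards it to the coordinating center. One seriousness criterion is "Causes hospitalization or prolongs hospital stay".

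On visits, section 7.2 schedules six doctor control visits after baseline, two per stage, the last being "2 follow-up visits during the maintenance up to the 2-year completion". Dietitian visits are fortnightly in ketosis, then "monthly during the physiological adaptation of stage 2 and quarterly or semi-annual during the maintenance stage". The doctor may add visits at discretion. Section 6 separately has the doctor seeing the patient every fortnight in the ketogenic stage.

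Side effects and serious reactions are secondary endpoints (section 9.2). The safety paragraph at the end of section 10.2 plans a descriptive analysis of everything patients report during the study. Admissions are part of the primary endpoint on resource use (section 9.1), and admission days enter healthcare expenditure (section 10.2).

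**The concern.** The staff explicitly asked to record admissions are not the staff who judge whether an event is a serious reaction, and the supplied text does not connect the two records. A reaction mentioned to a dietitian falls within the planned safety analysis but has no designated field on the dietitian list. A treatment-related admission entered by a dietitian can reach the expenditure analysis without a seriousness assessment.

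Weight and blood pressure are on the dietitian list and tolerability is not, so after ketosis benefit is measured more often than harm. A low late side-effect rate could then not be told apart from under-recording. Patients who withdraw before their next doctor visit are the most exposed. The study completion form asks the doctor for the date of and reason for dropout, which captures a side effect only if it is given as the reason.

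**Working it through.** The plan gives no figure to reproduce. The check counts scheduled contacts from the stage lengths in section 6 and the frequencies in section 7.2.

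**Stage lengths.** Initial BMI 30 to 35: stage 1 lasts 2 months and stage 2 lasts 4, so maintenance is 24 − (2 + 4) = 18 months. Initial BMI > 35: 3 and 6 months, so maintenance is 24 − (3 + 6) = 15 months.

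**Doctor gaps in maintenance.** Two visits, assumed evenly spaced with the last at month 24: 18/2 = 9 months, or 15/2 = 7.5 months.

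**Doctor gaps in stage 2.** Section 7.2 places the first stage 2 visit at month 4 or 5 and the second at the end of the stage. Counting from treatment start, and assuming month 4 applies to BMI 30 to 35 and month 5 to BMI > 35:
- BMI 30 to 35: visits at months 2, 4 and 6, so gaps of 2 and 2 months.
- BMI > 35: visits at months 3, 5 and 9, so gaps of 2 and 4 months.

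**Contacts after ketosis.** Dietitian visits are one per month in stage 2, then one every 6 or every 3 months in maintenance, rounded down. Scheduled doctor visits are 2 + 2 = 4.

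| | BMI 30 to 35 | BMI > 35 |
|---|---|---|
| Dietitian, stage 2 | 4 | 6 |
| Dietitian, maintenance | 18/6 = 3 to 18/3 = 6 | 15/6 → 2 to 15/3 = 5 |
| Dietitian, total | 7 to 10 | 8 to 11 |
| Doctor, total | 4 | 4 |

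**Share of scheduled contacts without a side-effect item.** Let D be the number of dietitian visits.
- If doctor and dietitian visits never coincide, the share is D/(D + 4): 7/11 = 64% at the low end, 11/15 = 73% at the high end.
- If all four doctor visits fall on dietitian visit days, the share is (D − 4)/D: 3/7 = 43% to 7/11 = 64%.

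The overall range is 43% to 73%. Unscheduled doctor visits would lower it.

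**Ketogenic stage.** Fortnightly dietitian visits number about 4 in 2 months or 6 in 3 months. Section 6 gives the doctor the same frequency; section 7.2 schedules two control visits. On the section 6 reading the two groups see the patient equally often in this stage.

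**The case against.** The case on the other side is substantial, and most of it limits the point.

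- **Ketosis.** If the doctor sees the patient fortnightly, dietitians have no advantage in contact during the most restrictive stage. This stands. Moreover, section 9.2 words the serious-reaction endpoint in terms of the protein diet's follow-up, which may be narrower than the whole study. But the side-effect endpoint has no such limit, and section 11 covers the entire follow-up.
- **Stage 2.** A reader might infer that side effects in stage 2 as well as maintenance rest on many months of recall. The visit schedule does not support that for stage 2, where gaps are about 2 to 4 months.
- **Maintenance.** With semi-annual dietitian visits the contrast nearly vanishes: 3 or 2 dietitian visits against 2 doctor visits. The larger post-ketosis totals then come mostly from monthly visits in stage 2, where doctor gaps are short.
- **The doctor's record.** It includes complications, and an admission is not easily forgotten. A reader might infer that an admission noted by a dietitian will never be assessed. Late capture at the next check-up is at least as plausible.
- **Missing text.** A reader might infer that the plan has no hand-over or reconciliation at all. That cannot be established, because part of section 8 and the forms in Annexes 3 and 5 were not available. What can be said is that section 11, where a hand-over would be expected, states none.
- **Events versus reactions.** Section 11 concerns suspected reactions. An unrelated admission properly counts as expenditure and is properly absent from the reaction listing. A mismatch alone is not an error; only related admissions left unassessed matter, and their number cannot be estimated from the documents.

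What remains is that the dietitian list has no field for side effects and the supplied text names no route from that list to the physician.

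**Conclusion.** The point holds in a limited form. Followed as written, the procedures allow side effects told to dietitians to be recorded late or missed, and allow a treatment-related admission to be costed without a seriousness assessment. The exposure is mainly in maintenance (doctor gaps of about 7.5 to 9 months), smaller in stage 2, and small in ketosis if the fortnightly doctor visits take place and side effects are recorded at them. The figures rest on even spacing in maintenance, the stated reading of the stage 2 visit months, and scheduled visits only. The 43% to 73% describes contacts without a prompt for side effects; it is not an estimate of reactions lost.

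Safety is a secondary, descriptive objective, so this does not threaten the primary cost analysis. It does affect how far a low late side-effect rate can be believed, and it should be corrected because the remedy is cheap.

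**What to change.** 1. In section 7.2, add a side-effect item to the dietitian list, in the same terms as the doctor's.
2. In section 11, unless section 8 or the annexes already do so, state that admissions, complications and side effects recorded by a dietitian are passed promptly to the study physician, who assesses relatedness and seriousness and documents the result.
3. Before database lock, list all recorded admissions and confirm that each has a documented physician assessment. Admissions judged unrelated need no Serious Adverse Reaction form.
4. Reconcile section 6 (fortnightly doctor visits in the ketogenic stage) with section 7.2 (two control visits), and say at which of these visits side effects are recorded.

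The cost is one line on an existing form, a sentence in section 11, a listing before lock and a clarification of the visit schedule. No added visits or staff are required. The downside is a few more events for the physician to assess, and reported rates may rise because ascertainment improves.

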12. ETHICAL ASPECTS

12.1 General

This study will be carried out in accordance with current regulations, international accepted ethical standards of Good Clinical Practice (CPMP/ICH/135/95) and the principles established in the latest version of the Declaration of Helsinki.

12.2. Informed consent

Prior to inclusion in the study, the study doctor should provide the patient with information about the study (Annex 1), propose participation in the same, answer any questions and request the completion of the informed consent (Annex 2), which he/she will keep in his/her own files.

12.3. Confidentiality of data

The data of the different participating subjects will become part of a totally confidential electronic file owned by Pronokal Group.

